### **Prohibited Therapies and/or Medications**

28. Failed (no response, insufficient response, loss of response, and/or intolerance) > 4 approved biologic therapies (anti-TNF, anti-integrin, anti-IL12/23), whether of same or different mechanism of action.
29. Any marketed biologic within 8 weeks for anti-TNF agents and 12 weeks for anti-integrin agents (e.g., vedolizumab) and ustekinumab prior to Day 1 **or** if drug level per therapeutic dose monitoring is greater than lower limit of detection.
30. Any biologic immunomodulators used for CD or other conditions within 8 weeks or 5 half-lives, whichever is longer, prior to Day 1 **or** if drug level per therapeutic dose monitoring is greater than lower limit of detection.
31. Rituximab within 1 year prior to Day 1.
32. Parenteral corticosteroids within 4 weeks or rectal administration of corticosteroids within 2 weeks prior to Day 1.
33. Rectal administration of 5-ASA within 2 weeks prior to Day 1.
34. Tacrolimus, cyclosporine, mycophenolate mofetil (CellCept®), immunoadsorption columns (such as ProSORBA columns), D Penicillamine, Leflunomide, Thalidomide, chronic use of non-steroidal anti-inflammatory agents (NSAIDs), and use of aspirin > 81 mg/day within 2 weeks prior to Day 1.

35. Other investigational chemical agent within 30 days or other investigational biologic agent within 8 weeks or 5 half-lives (whichever is longer) of entry into the IP.

36. Prior exposure to PRA023.

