**Table 2 Schedule of Study Assessments – Induction Period**

Study Week	Study Visit							Early Termination	NOTES
	0	1	2	6	10	12			
	Study Day	1	8	15	43	71	85		
Visit window (days)	0	±1	±3	±3	±3	±3			
Procedure									
Eligibility Confirmation	X								
Randomization	X								Via IRT system
Complete Physical Examination						X	X		
Targeted Physical Examination	X		X	X	X				
Vital Signs	X	X	X	X	X	X	X		Heart rate, temperature, blood pressure; Take pre-dose (no more than 30 minutes pre-infusion), end of infusion, and end of observation period.
Weight	X	X	X	X	X	X	X		Needed for CDAI assessment
ECG	X					X	X		
Adverse Events Assessment	X	X	X	X	X	X	X		
Concomitant Medication	X	X	X	X	X	X	X		
Efficacy Assessments									
Ileocolonoscopy with Biopsy						X	X		Ileocolonoscopy to be performed within 10 days after Week 12 visit, or at early termination visit
Review eDiary Data from Subjects	X	X	X	X	X	X	X		Remind subjects to record in their eDiary daily
CDAI Assessment	X	X	X	X	X	X	X		
PDAI	X					X	X		
Fistula Drainage Assessment	X		X	X	X	X	X		
IBDQ	X			X		X	X		
Laboratory Testing									
CBC	X	X	X	X	X	X	X		
Chemistry Panel	X		X	X		X	X		
Fasting Lipid Panel	X					X	X		

	Study Visit							NOTES	
	Study Week	0	1	2	6	10	12		Early Termination
	Study Day	1	8	15	43	71	85		
Visit window (days)	0	±1	±3	±3	±3	±3			
Procedure									
Urinalysis	X		X	X		X	X		
Urine Pregnancy Test (WOCBP only)	X			X		X	X		
Pharmacokinetics	X a	X	X b	X b	X a	X	X	a. The PK sample at Week 0/Day 1 and Week 10 must be taken pre-dose, immediately following the end of infusion (within 30 minutes), and 1 hour after the end of infusion. b. The PK sample taken at Weeks 2 and 6 must be taken pre-dose (within 30 minutes prior to dosing).	
Immunogenicity	X a		X a	X a		X	X	a . To be taken pre-infusion	
Biomarkers									
Biomarkers	X		X	X	X	X	X	Serum at all visits; additional whole blood at Weeks 0, 6 and 12	
Soluble TL1A	X		X	X	X	X	X		
hsCRP	X	X	X	X	X	X	X		
Fecal Calprotectin	X			X		X	X		
Infusion	X		X	X	X			Include date, start and stop time, volume infused, and length of the IV infusion. Infusion observation period at Week 0/Day 1 and Week 2 will be 1 hour (2 hours for subjects in Czech Republic); 30 minutes for all subsequent infusions thereafter.	

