## **6.7 Immunogenicity (Anti-Drug Antibody)**

Antibodies to PRA023 will be evaluated in blood samples collected from all subjects at the time points specified in the protocol (see [Section 6.1.1](#)). The detection and characterization of antibodies to PRA023 will be performed using a validated assay method by the Sponsor or Sponsor's designee. Instructions for the handling of ADA samples will be provided in the Laboratory Manual.

Blood samples will be screened for antibodies binding to PRA023 and the titer of confirmed positive samples will be reported. If confirmed positive, antibodies may be further characterized and/or evaluated for their ability to neutralize the activity of PRA023. Other analyses may be performed to verify the stability of antibodies to PRA023 and/or further characterize the immunogenicity of PRA023.

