### **9.2.4 Evaluation of Immunogenicity**

The proportion of samples positive for ADA and the proportion of subjects with any sample positive for ADA will be summarized by dose, when appropriate, using descriptive statistics. The PRA023 concentrations from all subjects and subjects with no sample positive for ADA will be summarized to assess whether ADA has an impact on PRA023 exposure.

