To assess the proportion of subjects with normalization of fecal calprotectin (fecal calprotectin < ULN), among subjects with elevated concentrations at Baseline, at Week 12	
 Proportion of subjects with normalization of fecal calprotectin (as defined by fecal calprotectin < ULN), among subjects with elevated concentrations at Baseline, at Week 12
To assess the proportion of subjects with clinical improvement at Week 12	
 Proportion of subjects in clinical response, as defined by reduction in CDAI \geq 100 points from Baseline or CDAI < 150 at Week 12
To assess the proportion of subjects with two component patient-reported outcome (PRO-2) remission at Week 12	
 Proportion of subjects with PRO-2 remission (defined as average daily abdominal pain score \leq 1 point and average daily stool frequency \leq 3 points with abdominal pain and stool frequency no worse than Baseline) at Week 12
To assess the change in SES-CD score from Baseline to Week 12	
 Change in mean SES-CD score at Week 12 from Baseline
To assess the pharmacokinetics (PK) of PRA023	
 Descriptive summaries of PK and immunogenicity of PRA023
To assess the immunogenicity of PRA023	
 Proportion of subjects developing anti-drug antibody (ADA) and neutralizing antibody (Nab)
Exploratory	
To assess endoscopic remission at Week 12	
 Proportion of subjects with endoscopic remission, as defined as SES-CD \leq 4 and at least 2-point reduction from baseline and all individual score \leq 1 at Week 12
To assess ulcer-free at Week 12	
 Proportion of subjects with SES-CD ulcerated surface score of 0 at week 12 among patients with SES-CD ulcerated surface score \geq 1 at baseline
To assess the change in SES-CD segment score from baseline to Week 12	
 Change from baseline in SES-CD for each segment at Week 12

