6.3 SECONDARY EFFICACY ENDPOINTS

6.3.1 DICHOTOMOUS OR BINARY ENDPOINTS

The definition of the dichotomous secondary efficacy endpoints (i.e., responders) are listed in Table 3 below.

Table 3 Definition of Secondary Binary Endpoints

Outcome	Measure	Definition	Analysis Timepoints
Clinical Remission	CDAI	Crohn's disease activity index [CDAI] < 150	Week 12
Endoscopic and clinical improvement	SES-CD and CDAI	Decrease in SES-CD ≥ 50% AND reduction in CDAI ≥ 100 points from Baseline, or CDAI < 150	Week 12
Biomarker and Clinical Composite Improvement	hsCRP and CDAI	Decrease in hsCRP or fecal calprotectin ≥ 50% from Baseline and reduction in	Week 12

		CDAI \geq 100 points from Baseline, or CDAI < 150	
Clinical Response	CDAI	Reduction in CDAI \geq 100 points from Baseline or CDAI < 150	Week 12
PRO-2 remission	Abdominal pain score and Stool frequency	Average daily abdominal pain score \leq 1 point and average daily stool frequency \leq 3 points with abdominal pain and stool frequency no worse than Baseline	Week 12
Normalization of hsCRP	hsCRP	hsCRP < ULN, among subjects whose baseline hsCRP \geq ULN	Baseline, Week 12
Normalization of fecal calprotectin	fecal calprotectin	fecal calprotectin < ULN, among subjects whose baseline fecal calprotectin \geq ULN	Week 12
Anti-drug antibody (ADA) and Neutralizing antibody (Nab)	ADA and Nab	Positive ADA at any time; Positive Nab at any time	Over time

Abbreviations: SES-CD, Simple endoscopy score for Crohn's disease; CDAI, Crohn's disease activity index; hsCRP, High sensitivity C-reactive protein; PRO-2, Two component patient-reported outcome; ADA, Anti-drug antibody; Nab, Neutralizing antibody.

The proportion of clinical remission in FAS will be analyzed according to the method similar to the sensitivity analysis for the primary efficacy endpoint, in the case of missing data in CDAI at Week 12. If the resulting lower limit of 95% confidence interval is greater than 16%, the observed remission rate for the placebo treated patients from multiple prior CD trials ([1], [7], [8], [9], [10]), the null hypothesis for the first secondary endpoint of clinical remission at Week 12 will be rejected at a 1-sided significance level of 0.025.

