6.7 EVALUATION OF IMMUNOGENICITY

The proportion of subjects with any sample positive for ADA and the proportion of subjects with any sample positive for neutralizing antibody (Nab) will be summarized by the study period and dose using descriptive statistics. The PRA023 concentrations from all subjects and subjects with no sample positive for ADA will be summarized to assess whether ADA has an impact on PRA023 exposure.

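### The rule for subjects developing ADA or Nab does not exclude the pre-dose Week 0 sample, so a subject positive before any drug can be counted as a new case

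*SAP*

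**What the plan says.** **The endpoint.** SAP Section 2, Table 1, gives it as "Proportion of subjects developing anti-drug antibody (ADA) and neutralizing antibody (Nab"). Protocol 3.2 uses the same wording.

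**The counting rule.** SAP Table 3 in Section 6.3.1 defines a positive as "Positive ADA at any time; Positive Nab at any time". SAP 6.7 summarizes "The proportion of subjects with any sample positive for ADA" and has a matching proportion for Nab, by study period and dose. Protocol 9.2.4 has the same rule for ADA: "the proportion of subjects with any sample positive for ADA will be summarized by dose".

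**The samples.** Protocol Table 2 and SAP Appendix G both mark immunogenicity at Week 0/Day 1, with the footnote "To be taken pre-infusion". Further induction samples follow at Weeks 2 and 6 (also before infusion), Week 12 and early termination.

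**Related provisions.** The exclusion criteria include "Prior exposure to PRA023". Protocol 6.7 says that "the titer of confirmed positive samples will be reported"; further testing of confirmed positives for neutralizing activity is optional. SAP 4.1 defines baseline in general as the last non-missing assessment before first dose, but no ADA or Nab rule uses it.

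**The concern.** Developing an antibody describes something that happens after exposure. A rule that accepts any positive sample at any time measures prevalence over the whole sampling period, including the time before exposure. The two agree only if nobody is positive at Week 0.

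Two kinds of subject separate them: one who is positive only before dosing, and one who is positive before and after dosing with no rise in titre. Neither has developed ADA, and both count under the written rule.

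At stake is the reported immunogenicity rate of a new antibody in a single-arm study of about 50 subjects, where a few subjects move a small percentage noticeably. Two other summaries depend on an ADA classification that the SAP does not define: the ADA status subgroup in 6.2.2 and the adverse events in immunogenicity-positive subjects in 7.1.6.1.

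**Working it through.** The plan states no ADA rate, precision or power, so there is no figure to reproduce. The check compares the texts and then illustrates the size.

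**1. Does the rule reach the Week 0 sample?**
- The sample exists and is drawn before the first infusion (Protocol Table 2; SAP Appendix G).
- Table 3 sets no start time. SAP 6.7 and Protocol 9.2.4 admit any sample.
- No section of either document limits the count to post-dose samples, excludes baseline-positive subjects, or defines treatment-induced, treatment-boosted or treatment-emergent antibody.
- The split by study period in SAP 6.7 does not isolate the sample, because Week 0 sits in the induction block of SAP Table 2 and of Appendix G.

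**2. Could a Week 0 positive have been induced by the study drug?** No. Prior exposure is excluded and the sample precedes the first infusion.

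**3. Does the SAP condition on baseline elsewhere?** Yes. In the same Table 3, normalization of hsCRP and of fecal calprotectin is limited to subjects elevated at baseline. In 7.1.6.1, an adverse event is treatment-emergent only if it starts or worsens on or after first dose. The ADA and Nab row has no such condition.

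**4. Size.** Inputs: N = 50 (planned, SAP 3.2); q = proportion positive at Week 0 (assumed, 0% to 10%); t = post-dose incidence among baseline-negative subjects (assumed, 10%).
- Any-time proportion = q + (1 − q)t
- Treatment-induced proportion = (1 − q)t
- Expected excess = 50q
- Chance of at least one Week 0 positive = 1 − (1 − q)^50

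| q | Any-time | Treatment-induced | Excess of 50 | Chance of at least one |
|---|---|---|---|---|
| 0% | 10.0% | 10.0% | 0 | 0% |
| 2% | 0.02 + 0.98 × 0.10 = 11.8% | 9.8% | 1.0 | 64% |
| 5% | 0.05 + 0.95 × 0.10 = 14.5% | 9.5% | 2.5 | 92% |
| 10% | 0.10 + 0.90 × 0.10 = 19.0% | 9.0% | 5.0 | 99.5% |

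The excess does not depend on t. It is an upper bound: if a fraction b of Week 0 positives have a genuine titre rise on treatment, they belong in the count and the excess falls to 50q(1 − b). With q = 10% and an assumed b = 50%, that is 50 × 0.10 × 0.50 = 2.5 subjects.

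**The case against.** **The SAP never says that the Week 0 sample counts.** A programmer could read the word developing together with the general baseline convention and use post-dose samples only. That is possible, but it requires setting aside the explicit definition in Table 3, which is the text that would normally be programmed. The mismatch stands.

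**The effect may be nil.** The documents give no pre-dose positivity, and it could be zero. This stands. A reader might infer that the reported rate is certain to be biased upward, or that pre-existing reactivity will be labelled as drug-induced. The documents support neither: the first depends on a rate that nobody has stated, and the second uses a label that neither document contains.

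**The subgroup and adverse event summaries may use another flag.** This also stands. A reader might infer that the Table 3 rule feeds both. But 6.2.2 says only positive or negative, 7.1.6.1 refers to subjects considered positive, and neither cites Table 3. What can be said is that the status is undefined there.

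**The exposure comparison is sound as planned.** SAP 6.7 compares concentrations in all subjects with those in subjects who have no ADA-positive sample. For the question of whether antibody affects exposure, keeping every antibody-positive subject out of the ADA-free group is reasonable, whatever the antibody's origin. A treatment-emergent flag would return pre-existing positives without a titre rise to that group. It would be tempting to count this comparison as a further error, but it is not one.

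**The damage is limited and recoverable.** The endpoint is descriptive, the testing hierarchy in SAP 6.10 covers only endoscopic improvement and clinical remission, and individual data listings and titres would allow reclassification afterwards. This limits the importance of the point. It does not justify leaving a rule that disagrees with its own endpoint, since the definition should be fixed before results are seen.

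**Conclusion.** The point holds as a mismatch between endpoint and definition. Read literally, SAP Table 3 and 6.7 count a subject who is positive only before the first dose as having developed ADA or Nab. The ADA rate is overstated by the number of Week 0 positives without a true titre rise: 0 to 5 of 50 at an assumed pre-dose positivity of 0% to 10%. The text mismatch is certain; the size rests wholly on that assumed range. No primary or tested conclusion changes. The point does not extend to the exposure comparison. For the subgroup and adverse event summaries, it goes no further than noting that the ADA classification is unstated.

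**What to change.** Amend SAP Table 3 and 6.7 as follows.

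- **Treatment-emergent ADA:** baseline negative or missing with at least one post-dose positive, or baseline positive with a post-dose titre rise of a size fixed in advance. Limiting the count to post-dose samples is not enough on its own, because a persistent baseline positive would still count.
- **Treatment-emergent Nab:** post-dose Nab positive and not Nab positive at baseline. A titre rule does not carry over to Nab. Because Protocol 6.7 makes neutralization testing optional, state that the baseline sample is Nab-tested whenever it is ADA-confirmed.
- **Denominator and baseline:** state the evaluable denominator for each proportion and report baseline prevalence separately.
- **Other uses:** state which flag defines ADA status in 6.2.2 and immunogenicity positive in 7.1.6.1. Leave the 6.7 exposure comparison as it is.

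The cost is SAP wording and one derived flag for each antibody. Week 0 samples and titres of confirmed positives are already planned, so ADA needs no new data. The only possible extra laboratory work is Nab testing of ADA-confirmed baseline samples. As the SAP is already final, its Section 1 also requires the change and its rationale to be documented in the clinical study report.

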6.3.2 CONTINUOUS ENDPOINTS

The mean change from baseline in SES-CD score at Week 12 for PP analysis set will be estimated using ANCOVA with baseline SES-CD score as covariates. The 95% confidence interval for the LS mean for the change from baseline at Week 12 will be calculated. The median for the change from baseline in SES-CD score at Week 12 for PP analysis set will also be estimated and p-value for testing against no change will be reported using Wilcoxon rank test.

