3.2 DETERMINATION OF SAMPLE SIZE

The study is planned to enroll approximately 50 subjects. The sample size will enable a statistical power of 80%, at 1-sided significance level of 0.025, to test against the null hypothesis of endoscopic improvement rate of 12%, assuming the endoscopic improvement rate for PRA023 is 27%.

The null hypothesis of an endoscopic improvement (decrease in SES-CD $\geq 50\%$) rate of 12% is based on a meta-analysis estimate of the upper limit of 95% CI of the observed placebo rate (95% CI) of 9.5% (7.1, 11.9) from multiple modern-era CD clinical trials with centrally read endoscopy and similar eligibility criteria. [1]

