3.3 RANDOMIZATION

3.3.1 RANDOMIZATION NUMBERS

This is an open-label study where all subjects will receive PRA023. Eligible subjects will be assigned a subject number by the IRT system at Week 0/Day 1 upon confirmation of study eligibility as a means to track the number of eligible subjects enrolled in the study. Subjects who are randomized in OLE will retain their original subject numbers.

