4 GENERAL CONSIDERATIONS FOR DATA ANALYSES

4.1 REPORTING CONVENTIONS

The following reporting conventions apply generally to tables, listings, and graphs:

- Unless otherwise specified, the baseline value is defined as the last non-missing assessment before the first does of study treatment.
- If the date of interest occurs on or after the first dose date, the study day will be calculated as (date of interest – date of first dose) + 1.
- If the date of interest occurred prior to the first dose date, then study day will be calculated as (date of interest – date of first dose).
- Categorical data will be summarized by treatment group in terms of frequency counts and percentages.
- Continuous variables will be summarized by treatment group using descriptive statistics (the number of subjects (n), mean, median, standard deviation (SD), minimum (Min), and maximum (Max)) of the values at each visit and the change from baseline to each visit, unless specified otherwise.
- Confidence Intervals (CIs) will be presented as 2-sided 95% CIs.
- All mean, median and CI values will be formatted to one more decimal place than the measured values. SD values will be formatted to two more decimal places than the measured value. Min and Max will be formatted to the same number of decimal places as the measured value. The maximum number of decimal places reported shall be four for any summary statistic.
- All percentages will be rounded to one decimal place, unless specified otherwise. The number and percentage of responses will be presented in the form xx (xx.x), where the percentage is in the parentheses.
- Change from baseline is calculated as a post-baseline value minus the baseline value.
- All laboratory data will be reported using standard international units.
- All analysis and summary tables will include the analysis population sample size (ie, number of subjects) in the column headings.

- By-subject listings will be presented for all subjects in the relevant analysis sets, and sorted by treatment allocation, study site (if applicable), Subject ID, date, and visit. Numeric data will be listed to the same number of decimal places as recorded on the eCRF or other data source. Data collected on log forms, such as AEs, will be presented in chronological order within the subject, and age, and sex will be included in the listing, as space permits.

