4.2.4 PER-PROTOCOL(PP) ANALYSIS SET

The PP analysis set is a subset of FAS. Subjects who had significant protocol deviations will be excluded from analysis based on PP analysis set.

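### The 95% CI for mean SES-CD change comes from a single-arm ANCOVA; it is valid conditional on the observed baselines but too narrow for the population mean change, by an amount the documents do not fix

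*SAP*

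**What the plan says.** The endpoint is secondary and is listed in SAP Section 2 as "Change in mean SES-CD score at Week 12 from Baseline". Section 6.3.2 analyses it in the per-protocol (PP) set. The mean change is to be "estimated using ANCOVA with baseline SES-CD score as covariates", followed by this sentence: "The 95% confidence interval for the LS mean for the change from baseline at Week 12 will be calculated". Section 4.1 sets the level and sidedness: "Confidence Intervals (CIs) will be presented as 2-sided 95% CIs".

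Induction has a single arm. SAP Section 3.3.1 states: "This is an open-label study where all subjects will receive PRA023". The model therefore has an intercept and a slope on baseline, and no treatment factor.

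The same section of the SAP also plans the median change, with a "p-value for testing against no change will be reported using Wilcoxon rank test". SAP Section 10 lists the ANCOVA among the changes from the protocol and gives no reason for it.

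The SAP does not say at which baseline value the LS mean is evaluated, or whether the interval is meant to be conditional on the observed baselines.

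**The concern.** In a two-arm trial, baseline adjustment removes noise from a comparison between groups. Here there is no comparison. The covariate leaves the estimate where it was and takes baseline variance out of the standard error. A second sample of patients would have a different mean baseline and, because baseline and change are correlated, a different mean change. The ANCOVA standard error does not count that variation.

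A reader of the study report will probably take the interval as a statement about patients with this disease. Read that way it claims more precision than the data carry. The report could also show two precisions for one number, because Section 4.1 plans the raw mean and SD of change unless otherwise specified.

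**Working it through.** **Inputs from the documents**
- One arm, with baseline SES-CD as the only covariate: SAP 3.3.1 and 6.3.2.
- Two-sided 95% interval: SAP 4.1.
- Sample size: "The study is planned to enroll approximately 50 subjects" (SAP 3.2). The analysis uses the PP set, and "The PP analysis set is a subset of FAS" (SAP 4.2.4), so its size is not known in advance.
- Entry floor on baseline: SES-CD at least 6, or at least 4 for isolated ileal disease (Protocol 4.2.1.1, criterion 4).

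**Assumed, because the documents are silent**
- LS mean evaluated at the observed baseline mean, the usual software default.
- n of 45 or 50.
- Correlation r between baseline and change from 0 to −0.7.
- Normal data for the main simulations.

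The SAP states no figure for this interval, so there is none to reproduce.

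**Step 1: the estimate.** Write d for change and x for baseline, with d = a + b·x + e. At the sample mean of x, the fitted value is the sample mean of d. An OLS fit to one simulated sample of 50 confirmed this: LS mean −4.478, raw mean change −4.478.

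**Step 2: the standard error.**
- ANCOVA: SD(residual)/√n, on n − 2 degrees of freedom.
- Population mean change: SD(change)/√n, on n − 1 degrees of freedom.
- Link: Var(d) = Var(residual) + b²·Var(x), and Var(residual) = (1 − r²)·Var(d).

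The ANCOVA version omits b²·Var(x)/n. In the same OLS sample the two standard errors were 0.751 and 0.806, a ratio of 0.751/0.806 = 0.93.

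**Step 3: relative width and coverage.**

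Width ratio = √(1 − r²) × √((n − 1)/(n − 2)) × t(0.975, n − 2)/t(0.975, n − 1)

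Large-sample coverage = 2Φ(1.96·√(1 − r²)) − 1

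Example, r = −0.5: √(1 − 0.25) = 0.866, and 1.96 × 0.866 = 1.70, so coverage is 91.0%. At n = 50 the small-sample terms raise the width ratio from 0.866 to 0.875.

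| r | Width ratio, n = 50 | Large-sample coverage | Simulated coverage, n = 45 |
|---|---|---|---|
| 0 | 1.011 | 95.0% | 95.1% |
| −0.2 | 0.990 | 94.5% | 94.6% |
| −0.3 | 0.964 | 93.8% | 93.8–94.0% |
| −0.4 | 0.927 | 92.8% | 92.6–93.0% |
| −0.5 | 0.875 | 91.0% | 91.2–91.5% |
| −0.6 | 0.809 | 88.3% | 88.4–89.0% |
| −0.7 | 0.722 | 83.8% | 84.5–84.6% |

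A range in the last column spans separate simulation runs. The paired t interval stayed at about 95% in these normal-data runs. At n = 50 the ANCOVA interval is narrower than the paired one only once |r| exceeds about 0.15.

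**Step 4: what r might be.** With c the correlation between baseline and Week 12, and k = SD(Week 12)/SD(baseline):

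r = (k·c − 1)/√(1 + k² − 2·k·c)

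For k = 1 and c = 0.5, r = −0.5/√1 = −0.5. Over k from 0.8 to 1.2 and c from 0.3 to 0.8, r runs from −0.06 to −0.71. The standard-error ratio then runs from 1.00 to 0.71, and large-sample coverage from about 95% to 83.5%. The shortfall in width is therefore anywhere from nil to about 29%.

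**Step 5: dependence on normality.** SES-CD is bounded (0 to 56, SAP 6.1.1) and baseline has a floor. In runs with assumed skewed baselines and proportional response, the ANCOVA interval covered about 87–94% and the paired interval about 94–95%.

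**The case against.** The strongest reply is that the SAP promises an interval for an LS mean, a model quantity conventionally read as conditional on the covariates. Read that way the interval is correct. This stands. A reader might infer that the interval is invalid outright, or that it misses the true mean change more than 5% of the time whatever is meant by that mean. The documents do not support either reading. The defect appears only when the target is the population mean change. What remains is that the SAP calls the target the mean change from baseline, does not say that the interval is conditional, and specifies no other interval for that mean.

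The size is also open to challenge. A reader might take 84–85% as the expected coverage. It is the far end of an assumed range, and a weak correlation would leave coverage close to 95%. A negative r is plausible, since change contains minus baseline and entry requires a minimum score, but nothing in either document fixes its value. If the LS mean were taken at some fixed baseline instead, the estimand would differ and would still be conditional.

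Finally, nothing is decided on this interval. The hierarchy in SAP 6.10 contains only the primary endpoint and clinical remission. The only p-value for this endpoint is the Wilcoxon one, which does not use the ANCOVA standard error. If the raw mean and SD of change are tabulated as SAP 4.1 generally plans, a reader could build the paired interval by hand. All of this limits the importance of the point. It does not supply a prespecified interval for the population mean change.

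**Conclusion.** The concern holds in a limited form. The planned interval is valid conditional on the observed baselines and too narrow for the population mean change by about √(1 − r²). The algebra is certain once the LS mean is taken at the observed baseline mean. The size is not: over the assumed r from 0 to −0.7, with n of 45 to 50 and normal data, coverage goes from about 95% to 84–85%.

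A reader might go on to infer that the trial's efficacy conclusion, or its finding on SES-CD change, is at risk. It is not: the point estimate is the raw mean change either way, and no success rule refers to this interval. This is a minor correction, worth making because it is nearly free.

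**What to change.** In SAP 6.3.2, define the 95% CI for mean SES-CD change at Week 12 as mean change ± t(0.975, n − 1) × SD(change)/√n, in the same analysis set. Keep the ANCOVA LS-mean interval only as supportive, state the baseline value at which it is evaluated, and label it as conditional on the observed baselines. Amend the matching entry in SAP Section 10.

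The cost is about one sentence in 6.3.2 and a somewhat wider interval. At n = 50 it would be about 4% wider at r = −0.3 (1/0.964 = 1.04), 14% at r = −0.5 (1/0.875 = 1.14) and 39% at r = −0.7 (1/0.722 = 1.39). No new data are needed. With bounded, skewed scores the paired interval may itself cover slightly under 95% (about 94–95% in the skewed runs), but it remained closer to nominal than the ANCOVA interval.
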